11.3 Early Termination of Subjects from the Study

Subjects are free to withdraw from the study at any time for any reason.

In addition, subjects may be withdrawn from the study by the PI or designee for the following reasons:

- AEs.
- Difficulties in blood collection.

A subject may be withdrawn by the PI (or designee) or the Sponsor if enrollment into the study is inappropriate, the study plan is violated, or for administrative and/or other safety reasons.

Subjects who withdraw from the study early following dosing will be requested to remain confined to the [REDACTED] at least until Day 8.

11.4 Lifestyle Considerations

11.4.1 Medications and Supplements Restrictions

Prior concomitant medications (including prescription and non-prescription medications, herbal remedies, or vitamin supplements) will be prohibited as listed in the exclusion criteria in [Section 11.2](#) and throughout the study.

After dosing, acetaminophen (up to 2 g per 24 hours) may be administered at the discretion of the PI or designee.

A mild laxative (i.e., Milk of Magnesia®, Colace®) or prune juice may be used to help with bowel movements if necessary, at the discretion of the PI/designee, except for the first 4 hours postdose.

Eye drops for retinal examination will be permitted to facilitate the ophthalmic assessments.

If deviations occur, the PI or designee in consultation with the Sponsor if needed will decide on a case by case basis whether the subject may continue participation in the study.

All medications taken by subjects during the course of the study will be recorded.

11.4.2 Meals and Dietary Restrictions

11.4.2.1 Meals

Water (except water provided with dosing) will be restricted 1 hour prior to and 1 hour after dosing, but will be allowed ad libitum at all other times. Other fluids may be given as part of meals and snacks but will be restricted at all other times throughout the confinement period.

Subjects will fast overnight for at least 10 hours prior to dosing. Subjects will continue the fast for at least 4 hours postdose.

When confined, standard meals and snacks will be provided at appropriate times, except when they are required to fast. When confined in the [REDACTED], subjects will be required to fast from all food and drink except water between meals and snacks (with exception for mild laxative [i.e., Milk of Magnesia®, Colace®] or prune juice which may be given at the discretion of the PI/designee at any time excluding the first 4 hours following dosing).

Each meal and/or snack served at the [REDACTED] will be standardized and will be similar in caloric content and composition and will be taken at approximately the same time.

11.4.2.2 Dietary Restrictions

The consumption of foods and beverages containing the following substances will be prohibited as indicated:

- Grapefruit/Seville orange (or products containing these): 14 days prior to dosing and throughout the period of sample collection.

11.4.3 Caffeine, Alcohol, and Tobacco Restrictions

Subjects will refrain to use the following:

- Xanthines/Caffeine-containing foods or beverages: 24 hours prior to dosing and throughout the period of sample collection (small amounts of caffeine derived from normal foodstuffs e.g., 250 mL/8 oz./1 cup decaffeinated coffee or other decaffeinated beverage, per day, with the exception of espresso; 45 g/1.5 oz. chocolate bar, per day, would not be considered a deviation to this restriction).
- Alcohol-containing foods or beverages: 48 hours prior to dosing and throughout the period of sample collection.
- Tobacco/nicotine containing products: at least 3 months prior to dosing and throughout the period of sample collection.

11.4.4 Activity Restrictions

Subjects will remain ambulatory or seated upright for the first 4 hours postdose, except when they are supine or semi-reclined for study procedures. Should AEs occur at any time, subjects may be placed in an appropriate position or will be permitted to lie down on their right side.

Specific measures will be taken to prevent the subject from missing a urine collection by strictly controlling and providing access to designated restrooms only. Subjects will be asked to void prior to entering the shower.

Subjects will be instructed to refrain from strenuous physical activity which could cause muscle aches or injury, including contact sports at any time from the Screening visit until completion of the study.

Should any subject withdraw or be withdrawn from the study, he will be cautioned against activities requiring mental alertness, judgment and physical coordination such as driving, operating machinery, or power equipment for a period of 24 hours postdose.

11.4.5 Contraception Requirements

11.4.5.1 Guidance for Subjects

Subjects must agree to the following method of contraception:

A non-vasectomized subject must agree to use a condom with spermicide or abstain from sexual intercourse during the study from dosing until 90 days after dosing. No restrictions are required for a vasectomized subject provided his vasectomy has been performed 4 months or more prior to dosing.

A subject who has been vasectomized less than 4 months prior to dosing must follow the same restrictions as a non-vasectomized subject.

The subject must agree not to donate sperm from dosing until 90 days after dosing.

CONFIDENTIAL

CT1812, CA35306, Final Protocol, Amendment 1_15Dec2021

12 TREATMENTS

12.1 Treatments Administered

Study drug will be supplied as capsules of nonradiolabeled CT1812 (powder) and capsules of radiolabeled [¹⁴C]-CT1812 (powder/suspension).

The study treatment will consist of 3 capsules: 2 capsules containing CT1812 (███████████) and 1 capsule containing ~1 µCi [¹⁴C]-CT1812 (███████████).

Capsules will be administered orally under fasting conditions on Day 1 at Hour 0 with approximately 240 mL of water. Additional water, up to 50 mL, is permissible to facilitate swallowing multiple capsules.

The pharmacy at the █████ will provide the [¹⁴C]-CT1812 dose in individual unit dose containers for each subject.

Subjects will be instructed not to crush, split, or chew the capsules.

The exact clock time of dosing will be recorded.

12.2 Dose Modification

The dose and administration of the study drug to any subject may not be modified. If necessary a subject must be discontinued for the reasons described in [Section 11.3](#).

12.3 Method of Treatment Assignment

Each subject will be assigned a unique identification number upon the Screening visit. Subjects who complete the study screening assessments and meet all the eligibility criteria will be assigned a unique identification number at the time of dosing, different from the screening number.

If replacement subjects are used, the replacement subject number will be 100 more than the original (e.g., Subject No. 101 will replace Subject No. 1). Subjects will be replaced at the discretion of the Sponsor if less than 6 subjects are available for evaluation.

12.4 Blinding

This is an open-label study.

12.5 Treatment Compliance

A qualified designee will be responsible for monitoring the administration of the timed oral doses. A mouth check will be performed by the qualified designee to ensure that the subjects have swallowed the study drug. Once a subject has finished the dosing water, the qualified designee will use a flashlight and a tongue depressor to check the subject's mouth. Subjects' hands will also be verified to ensure that the study drug was ingested.

13 STUDY ASSESSMENTS AND PROCEDURES

The Study Events Flow Chart ([Section 6](#)) summarizes the clinical procedures to be performed at each visit. Individual clinical procedures are described in detail below. Additional evaluations/testing may be deemed necessary by the PI or designee and/or the Sponsor for reasons related to subject safety.

For this study, the blood (for whole blood and/or plasma), urine, and feces collections for TRA, the blood (for plasma) CT1812 and M6 concentrations, and the blood (for plasma), urine, and feces collections for metabolite profiling, as applicable, are the critical parameters and need to be collected as close to the exact time point as possible. All other procedures should be completed as close to the prescribed/scheduled time as possible, but can be performed prior or after the prescribed/scheduled time.

Any nonscheduled procedures required for urgent evaluation of safety concerns take precedence over all routine scheduled procedures.

13.1 Screening

Within 28 days prior to dosing, medical history and demographic data, including name, sex, age, race, ethnicity, body weight (kg), height (cm), BMI (kg/m²) and history of tobacco use will be recorded. Each subject will have a 12-lead ECG, vital sign measurements (pulse rate, blood pressure, temperature, and respiratory rate), clinical laboratory tests, ophthalmic, C-SSRS, and physical examination.

13.2 Safety Assessments

13.2.1 Physical Examination

Full and abbreviated physical examinations and symptom driven physical examination(s) will be performed as outlined in the Study Events Flow Chart ([Section 6](#)). Additional symptom-driven physical examinations may be performed at other times, if deemed necessary by the PI or designee.

An abbreviated physical examination will include at the minimum, examination of respiratory, cardiovascular, and GI systems, with the option for further examination of additional systems as necessary based on reported symptoms/AEs.

13.2.2 Standard Vital Signs

Single measurements of body temperature, respiratory rate, blood pressure, and pulse rate will be measured as outlined in the Study Events Flow Chart ([Section 6](#)). Additional vital signs may be taken at any other times, if deemed necessary by the PI or designee.

Blood pressure and heart rate measurements will be performed with subjects in a seated position, except when they are supine or semi-reclined because of study procedures and/or AEs (e.g. nausea, dizziness) or if deemed necessary by the PI or designee.

Vital signs will be measured within 24 hours prior to Day 1 dosing for the predose time point. When scheduled postdose, vital signs will be performed within approximately 15 minutes of the scheduled time point.

13.2.3 ECG Monitoring

Single 12-lead ECGs will be performed as outlined in the Study Events Flow Chart ([Section 6](#)). Additional ECGs may be taken at any other times, if deemed necessary by the PI or designee.

ECGs will be performed with subjects in a supine position. All ECG tracings will be reviewed by the PI or designee.

ECGs will be measured within 24 hours prior to Day 1 dosing for the predose time point. When scheduled postdose, ECGs will be performed within approximately 20 minutes of the scheduled time point.

13.2.4 Ophthalmic Examinations

Ophthalmic examinations will be performed as outlined in the Study Events Flow Chart ([Section 6](#)). Additional ophthalmic examinations may be taken at any other times, if deemed necessary by the PI or designee. Ophthalmic examinations will include the following tests:

- Best-corrected visual acuity using Early Treatment Diabetic Retinopathy Study (ETDRS) charts (refraction only required if subjects does not have his corrective lenses or contact lenses)
- Slit lamp exam
- Intraocular pressure measurement with applanation tonometry
- Dilated fundus retinal exam

13.2.5 Body Weight

Body weight (kg) will be reported as outlined in the Study Events Flow Chart ([Section 6](#)).

13.2.6 Columbia Suicide Severity Rating Scale

The C-SSRS is a questionnaire scale to detect emergent suicide symptoms (suicidal ideation or actual suicidal behavior) during the course of this study. Assessments will be performed according to the Study Events Flow Chart ([Section 6](#)). At Screening, the C-SSRS Baseline/Screening version will be administered; at all other time points, as applicable, the Since Last Visit version will be administered. Additional C-SSRS assessments may be performed at other times if deemed necessary. The C-SSRS is to be administered at the site by an appropriately qualified/trained individual and a copy of the questionnaire to be used will be kept in the study binder. In addition, subjects who at any time during this study spontaneously report AEs of suicidal ideation or suicidal behavior, either as an outpatient or during visit interviews, must be assessed by the PI or designee and referred for further mental health evaluation as clinically indicated.

13.2.7 Clinical Laboratory Tests

All tests listed below will be performed as outlined in the Study Events Flow Chart ([Section 6](#)). In addition, laboratory safety tests may be performed at various unscheduled time points, if deemed necessary by the PI or designee.

Hematology

- Hemoglobin
- Hematocrit
- Total and differential leukocyte count
- Red blood cell count
- Platelet count

Serum Chemistry *

- Blood Urea Nitrogen
- Bilirubin (total and direct)
- Alkaline phosphatase
- Aspartate aminotransferase
- Alanine aminotransferase
- Albumin
- Sodium
- Potassium
- Chloride
- Calcium
- Glucose (fasting)
- Creatinine **
- Lactic dehydrogenase
- Creatine phosphokinase

Urinalysis

- pH
- Specific gravity
- Protein ***
- Glucose
- Ketones
- Bilirubin
- Blood ***
- Nitrite***
- Urobilinogen
- Leukocyte esterase ***

Additional Tests

- HIV test
- HBsAg
- HCV
- Urine drug screen
 - Opiates
 - Amphetamines
 - Barbiturates
 - Benzodiazepines
 - Cocaine
 - Cannabinoids
- Urine alcohol screen
- Urine cotinine

* Serum chemistry tests will be performed after at least an 8-hour fast; however, in case of dropouts or rechecks, subjects may not have fasted for 8 hours prior to the serum chemistry sample is taken.

** At the Screening visit, creatinine clearance will be calculated using the CKD-EPI formula.

*** If urinalysis is positive for protein, blood, nitrite and/or leukocyte esterase, a microscopic examination (for red blood cells, white blood cells, bacteria, casts, and epithelial cells) will be performed.

13.2.8 Adverse Events

13.2.8.1 Adverse Event Definition

An AE means any untoward medical occurrence associated with the use of a drug in humans, whether or not considered drug related.

A suspected adverse reaction means any AE for which there is a reasonable possibility that the drug caused the AE. Reasonable possibility means there is evidence to suggest a causal relationship between the drug and the AE.

An AE can therefore be any unfavorable and unintended sign (including an abnormal laboratory finding), symptom, or disease temporally associated with the use of a medicinal (investigational) product, whether or not related to the medicinal (investigational) product.

13.2.8.2 Monitoring

Subjects will be monitored for adverse reactions to the study formulations and/or procedures throughout the study, from the time of signing the ICF until the follow-up contact. Prior to release, subjects will be asked how they are feeling. At the follow-up contact, subjects will be queried with an open-ended question such as: 'How have you been feeling since your last visit?'

AEs (whether serious or non-serious) and clinically significant abnormal laboratory test value(s) will be evaluated by the PI or designee and treated and/or followed up until the symptoms or value(s) return to normal, or acceptable levels, as judged by the PI or designee.

Treatment of serious adverse events (SAEs) will be performed by a licensed health care professional, either at Celerion or at a nearby hospital emergency room where appropriate medical test(s) and/or examination(s) will be performed to document resolution of event(s). Outcome may be classified as fatal, not recovered/not resolved recovered/resolved, recovered/resolved with sequelae, recovering/resolving.

13.2.8.3 Reporting

All AEs that occurred during this clinical study will be recorded. All clinically significant abnormal laboratory results should be reported as AEs.

The PI or designee will review each event and assess its relationship to drug treatment (likely, probably, possibly, unlikely or unrelated).

Each sign or symptom reported will be graded on a 3-point severity scale (mild, moderate, or severe), and the date of onset, time of onset, and outcome of each event will be noted.

The following definitions will be used for rating the severity of AEs:

- | | |
|----------|---|
| Mild | The AE is easily tolerated and does not interfere with daily activity. |
| Moderate | The AE interferes with daily activity, but the subject is still able to function. Medical intervention may be considered. |
| Severe | The AE is incapacitating and requires medical intervention. |

13.2.8.4 Serious Adverse Event

If any AEs are serious, as defined by the Food and Drug Administration (FDA) CFR, Chapter 21, special procedures will be followed. All SAEs will be reported to the Sponsor via fax or e-mail within one working day of becoming aware of the event, whether or not the serious events are deemed drug-related. All serious event reporting will adhere to 21 CFR 312.32 for Investigational New Drugs (IND) and to the Guidance for Industry and Investigators: Safety Reporting Requirements for INDs and BA/BE, dated December 2012. The institutional review board (IRB) will be notified of the Alert Reports as per FDA regulations.

A SAE is any AE or suspected adverse reaction that in the view of either the PI (or designee) or Sponsor, results in any of the following outcomes: Death, a life-threatening adverse event, inpatient hospitalization or prolongation of existing hospitalization, a persistent or significant incapacity or substantial disruption of the ability to conduct normal life functions, or a congenital anomaly/birth defect. Important medical events that may not result in death, be life-threatening, or require hospitalization may be considered serious when, based upon appropriate medical judgment, they may jeopardize the patient or subject and may require medical or surgical intervention to prevent one of the outcomes listed in the above definition. Examples of such medical events include allergic bronchospasm requiring intensive treatment in an emergency room or at home, blood dyscrasias or convulsions that do not result in inpatient hospitalization, or the development of drug dependency or drug abuse.

Life-threatening is defined as an AE or suspected adverse reaction that in the view of the PI (or designee) or Sponsor, its occurrence places the patient or subject at immediate risk of death. It does not include an adverse event or suspected adverse reaction that, had it occurred in a more severe form, might have caused death.

Unexpected is defined as an AE or suspected adverse reaction that is not listed in the IB or is not listed at the specificity or severity that has been observed; or is not consistent with the risk information described in the general investigational plan or elsewhere in the current application, as amended.

If a SAE occurs to a subject on this study, contact the Sponsor personnel listed in [Section 3](#).

13.3 Pharmacokinetic Assessments

13.3.1 Blood Sampling and Processing

Blood samples for the determination of TRA in whole blood and plasma, CT1812 and M6 concentrations in plasma, and metabolite profiling in plasma will be collected at scheduled time points as delineated in the Study Events Flow Chart ([Section 6](#)).

Predose samples should be handled, processed, analyzed, and stored separately away from the postdose samples to avoid cross contamination.

Instruction for blood sampling, collection, processing, and sample shipment will be provided separately.

13.3.2 Pharmacokinetic Parameters

PK parameters for whole blood and plasma TRA concentration equivalents and for plasma CT1812 and metabolite M6, will be calculated, as appropriate:

AUC0-t:	The area under the concentration versus time curve, from time 0 to the time of the last common time point “t”, where t is the last common time point at which plasma TRA and plasma CT1812 are quantifiable in all subjects.
AUC0-24:	The area under the concentration versus time curve, from time 0 to the 24-hour time point.
AUC0-last:	The area under the concentration-time curve, from time 0 to the last observed non-zero concentration, as calculated by the linear trapezoidal method.
AUC0-inf:	The area under the concentration-time curve from time 0 extrapolated to infinity. AUC0-inf is calculated as the sum of AUC0-last plus the ratio of the last measurable concentration to the elimination rate constant.
AUC%extrap:	Percent of AUC0-inf extrapolated, represented as $(1 - AUC0\text{-last}/AUC0\text{-inf}) \times 100$.
Cmax:	Maximum observed concentration.
Tmax:	Time to reach Cmax. If the maximum value occurs at more than one time point, Tmax is defined as the first time point with this value.
Kel:	Apparent first-order terminal elimination rate constant calculated from a semi-log plot of the concentration versus time curve. The parameter will be calculated by linear least-squares regression analysis using the maximum number of points in the terminal log-linear phase (e.g., three or more non-zero concentrations).

t½:	Apparent first-order terminal elimination half-life will be calculated as 0.693/Kel.
CL/F:	Apparent total clearance after oral (extravascular) administration, calculated as Dose/AUC0-inf (parent only).
Vz/F:	Apparent volume of distribution during the terminal elimination phase after oral (extravascular) administration, calculated as Dose/(AUC0-inf x Kel) (parent only).

No value for Kel, AUC0-inf, AUC%extrap, CL/F, Vz/F, or t½ will be reported for cases that do not exhibit a terminal log-linear phase in the concentration-time profile.

No PK parameters will be calculated for subjects with 2 or fewer consecutive time points with detectable concentrations, or who have an AE of vomiting that occurs at or before 2 times the median Tmax.

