8.2 Rationale

8.2.1 Rationale for this Study and Study Design

The disposition of any drug in the body is controlled by physiological processes affecting absorption, metabolism, and excretion. The most efficient and well-established approach to elucidate these processes is a mass balance study in which the drug dose is administered in radiolabeled form, followed by collection and analysis of different biological matrices for radioactivity using liquid scintillation count and determination of drug concentration using conventional liquid chromatography-tandem mass spectrometry and metabolite profile using liquid chromatography with radiometric detection. The PK, metabolic pathways, and routes of elimination of CT1812 have been evaluated in vitro and in vivo in preclinical species (IB, Version 5.0). In this study the TRA of [¹⁴C]-CT1812 will be measured using accelerator mass spectrometry (AMS).

Additionally, the PK profile of CT1812 in humans has been evaluated in healthy subjects (in a SAD and MAD investigation [Study COG0101]). Currently, the biotransformation/metabolism and excretory pathways of CT1812 in humans are not known.

The aim of this study is to characterize the plasma exposure, clearance pathways, and excretion routes for CT1812 and its metabolites in healthy male subjects following oral administration. Based on data in healthy subjects, the average t_{1/2} of CT1812 following single oral administration in the fasted state for doses from 10 mg to 1120 mg (Study COG0101) ranged from 11.1 to 14 hours, thus, it is expected that more than 90% of the radioactivity should be eliminated within 168 hours postdose, the sampling duration in this study.

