13.3.8 Emesis

Collection containers (pre-weighed) for emesis will be available for subjects participating in the study at all times following dosing until discharge from the clinic. Subjects will be instructed at the beginning of the study that they should use one of the designated containers if emesis occurs following [¹⁴C]-CT1812 dosing. If emesis occurs following [¹⁴C]-CT1812 dosing and the subject has been able to collect the emesis in the designated container, it will be weighed and recorded, labeled with subject identification, time, and date, and analyzed for TRA. The subject may continue the study with permission from the Sponsor; however, subject data will be excluded from the PK or mass balance calculations if the AE of vomiting occurs at or before 2 times the median Tmax.

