13.3.10 Analytical Method

Samples from all subjects will be assayed even if the subjects do not complete the study.

Plasma concentrations of CT1812 and metabolite M6 will be determined using validated analytical methods. Whole blood, plasma, urine, and feces TRA will be determined with liquid scintillation counting or AMS detection. Profiling and identification of metabolites in plasma, urine, and where possible, feces will be conducted using standard laboratory procedures. Specifics of the analytical methods will be provided in separate documents.

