14.1 Sample Size Determination

The sample size of 8 healthy male subjects was selected without statistical considerations and in order to have complete data from 6 subjects available for evaluation. It has been determined adequate to meet the study objectives. This sample size is limited based on clinical considerations for this type of study and in order to limit exposure to radioactivity.

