14.2 Population for Analyses

PK Population: All subjects who comply sufficiently with the protocol and display an evaluable PK profile (e.g., exposure to treatment, availability of measurements and absence of major protocol violations or an AE of vomiting as described) will be included in the statistical analysis.

Safety Population: All subjects who received the dose of the study drug will be included in the safety analysis.

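### Could one subject whose plasma series ends early shorten AUC0-t for everyone?

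*Protocol*

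**What the plan says.** Protocol Section 13.3.2 lists several AUCs for TRA in whole blood and plasma and for CT1812 and M6 in plasma. AUC0-t is the only one whose end point in one subject depends on the other subjects' data: it stops at a common t, "where t is the last common time point at which plasma TRA and plasma CT1812 are quantifiable in all subjects". AUC0-24 has a fixed end, and AUC0-last and AUC0-inf use each subject's own data.

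The plan expects some incomplete subjects. Section 14.1 enrols 8 "in order to have complete data from 6 subjects available for evaluation". Section 12.3 adds: "Subjects will be replaced at the discretion of the Sponsor if less than 6 subjects are available for evaluation". Section 11.3 lists "Difficulties in blood collection" among the reasons for withdrawal, and Section 13.3.10 states: "Samples from all subjects will be assayed even if the subjects do not complete the study".

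Three provisions limit who enters the PK calculations:
- Section 14.2 defines the PK Population as "All subjects who comply sufficiently with the protocol and display an evaluable PK profile". Its examples of what makes a profile evaluable include having measurements available and having no major protocol violation.
- Section 13.3.2 gives no parameters to a subject with at most two detectable concentrations in a row, or with vomiting by twice the median Tmax.
- Section 13.3.8 says that in the vomiting case "subject data will be excluded from the PK or mass balance calculations".

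Section 14.3 leaves detailed methodology to a statistical analysis plan. The document supplied as the SAP covers the plasma assay only. It has no rule for AUC0-t, no analysis population and no rule for missing samples.

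**The concern.** A limit set by all subjects is set by the least favourable one. Up to two of the eight may be incomplete without triggering replacement, and their samples are still assayed. A man whose blood draws stop at 24 h for poor access has up to ten postdose samples, so he clears the two-point rule and could be judged evaluable. If his absent later samples count as not quantifiable, t is at most 24 h for everyone.

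Two analysts could then derive different t, and different AUC0-t values for every subject, from the same concentrations. The study is open-label and no rule is visible, so t could also be chosen after the data are seen. If the CT1812-to-TRA ratio were built on AUC0-t, and TRA fell more slowly than parent drug, a shorter window would raise the apparent parent share.

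**Working it through.** The plan states no figure to reproduce, since Section 14.1 chose 8 without statistical considerations. The check asks how far t could move and what that would change.

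**Inputs from the documents**
- Single-dose CT1812 half-life (Protocol 8.1.2): medians 11.1 to 14.0 h, fastest individual 7.1 h. Tmax is 60 to 90 minutes, midpoint 1.25 h.
- Sampling times (SAP Section 1): ..., 16, 24, 36, 48, 72, 96, 120, 144, 168 h.
- Incomplete subjects tolerated: 8 − 6 = 2.

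**Assumptions (not in the documents)**
- Mono-exponential decline.
- LLOQ at 1%, 0.1% or 0.01% of Cmax.
- One plasma series ending at 24 h.

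**Step 1: t without a truncated series.** The fastest eliminator sets it. Last quantifiable time ≈ 1.25 + 7.1 × log2(Cmax/LLOQ):
- ratio 100: 48.4 h, so t = 48 h
- ratio 1,000: 72.0 h, so t = 72 h
- ratio 10,000: 95.6 h, just before the 96 h draw, so t is still 72 h

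**Step 2: effect of moving t to 24 h.** The fraction of AUC0-inf captured is F(t,h) = 1 − 2^(−t/h). The fall in AUC0-t is 1 − F(24,h)/F(t,h).

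| Half-life h | F(24) | F(48) | F(72) | Fall from 48 h | Fall from 72 h |
|---|---|---|---|---|---|
| 11.1 h | 77.7% | 95.0% | 98.9% | 18.3% | 21.5% |
| 14.0 h | 69.5% | 90.7% | 97.2% | 23.4% | 28.5% |
| 50.6 h | 28.0% | 48.2% | 62.7% | 41.9% | 55.3% |

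The first two rows are CT1812 at its documented medians. For plasma TRA no half-life is given. If it tracked parent at 14 h, the fall would be 23.4 to 28.5%. The 50.6 h row is only illustrative: Section 8.2.1 says "it is expected that more than 90% of the radioactivity should be eliminated within 168 hours postdose", and 168/log2(10) = 50.6 h. That sentence concerns elimination from the body, so using it as a plasma half-life is an assumption.

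**Step 3: how often.** The chance that at least one of 8 series ends early is 1 − (1 − p)^8: 34% at p = 5% and 57% at p = 10%. Both rates are assumed. The 2-in-8 allowance (p = 25%, giving 90%) is not a rate for plasma series, because complete data also covers urine and feces, and early vomiters are already out. Section 11.2 excludes men with poor venous access, and Section 13 makes these blood draws critical parameters.

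**Step 4: what depends on t.**
- AUC0-24, AUC0-last, AUC0-inf and Cmax do not.
- Mass balance comes from urine and feces.
- Metabolite percentages come from the profiling data.
- At t = 24 h, AUC0-t simply equals AUC0-24, which is planned anyway.

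**The case for a change.** The strongest case for a change is that the wording is open and the trigger is foreseeable. Reading the PK Population into the definition does not close the gap, because Section 14.2 sets no completeness threshold and a series of ten postdose points could qualify. The SAP supplied is silent. TRA, CT1812 and M6 exposure serve primary objectives, and a sentence naming the population and the treatment of missing samples would cost nothing.

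Part of this stands: the text names no population and gives no rule for a missing draw. The rest carries less weight:
- Subjects who vomit early are excluded three times over (Sections 13.3.2, 13.3.8 and 14.2), and AUC0-t is a PK calculation.
- Availability of measurements is among the stated examples for evaluability, so letting one truncated series govern everyone is not the natural reading.
- The supplied SAP is a laboratory plan. The plan described in Section 14.3 is where this detail belongs, and it is not among the documents, so its silence cannot be assumed.
- The use of AUC0-t as an endpoint and the basis of the CT1812-to-TRA ratio are blacked out, so the effect on the parent share is conjecture.
- An obvious tightening, letting only subjects sampled through 168 h set t, would do harm. A fast eliminator who missed only the last draw could no longer set t. The common t could then pass his last quantifiable point, which defeats the definition.

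**Conclusion.** No change is needed. This is a gap that analysts fill sensibly: they determine t over the PK Population, do not treat a missing sample as one below the LLOQ, give no AUC0-t to a subject whose sampling stops before t while still quantifiable, and report t with the table.

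If the literal reading were applied and one series stopped at 24 h, CT1812 AUC0-t would be about 18 to 28% smaller. That rests on mono-exponential decline, median half-lives of 11.1 to 14.0 h and an assumed t of 48 to 72 h otherwise. For TRA the fall would be about 23 to 28% at 14 h, or 42 to 55% at an assumed 50.6 h. If no series ends before that t, the effect is nil. In every case the smaller figure is a correct AUC over a shorter window shared by both analytes, not a biased one, and the other exposure, recovery and metabolite results are unchanged.
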